1.1 TRIAL SUMMARY

Abbreviated Title	Pembrolizumab and Doxorubicin
Trial Phase	Phase I/II
Clinical Indication	Sarcoma
Trial Type	Single arm, open-label
Type of control	Historical
Route of administration	IV
Trial Blinding	None
Treatment Groups	Low and high dose doxorubicin/ phase I and phase II expansion
Number of trial subjects	maximum 47 (44 expected)
Estimated enrollment period	24 months
Estimated duration of trial	48 months
Duration of Participation	48 months

1.2 Table of contents:

1. Title

- 1.1 Trial Summary
- 1.2 Table of contents
- 1.3 Commonly Used Abbreviations

2. Trial Design

- 2.1 Introduction
- 2.2 Dosing Schedule
- 2.3 Management of Normal Doxorubicin Toxicity
- 2.4 Assessment of Response
- 2.5 Phase I Dose Escalation
- 2.6 Phase II Extension
- 2.7 Trial Diagram

3. Objectives

- 3.1 Primary Objectives and Hypothesis
- 3.2 Secondary Objectives and Hypothesis
- 3.3 Exploratory Objectives

4. Background and Rationale

- 4.1 Background
- 4.2 Rationale

5. Methodology

- 5.1 Entry Criteria
- 5.2 Trial Treatments
- 5.3 Concomitant Medications/Vaccinations (allowed & prohibited)

- 5.4 Rescue Medications & Supportive Care related to Pembrolizumab
- 5.5 Diet/Activity/Other Considerations
- 5.6 Subject Withdrawal/Discontinuation Criteria
- 5.7 Subject Replacement Strategy
- 5.8 Criteria for Early Trial Termination

- 6. Trial Flow Chart

- 7. Trial Procedures
 - 7.1 Trial Procedures
 - 7.2 Assessing and Recording Adverse Events
 - 7.3 Analysis of Biopsy Specimen

- 8. Statistical Analysis and Plan
 - 8.1 Statistical Analysis and Plan Summary
 - 8.2 Statistical Analysis Plan

- 9. Labeling, Packaging, Storage and Return of Clinical Supplies
 - 9.1 Investigational Product
 - 9.2 Packaging and Labeling Information
 - 9.3 Clinical Supplies Disclosure
 - 9.4 Storage and Handling Responsibilities
 - 9.5 Returns and Reconciliation

- 10. Administrative and Regulatory Details
 - 10.1 Institutional Review Board
 - 10.2 Consent
 - 10.3 Termination of Study
 - 10.4 Compliance with Trial Registration and Results Posting Requirements

10.5 Response Evaluation Criteria in Solid Tumors (RECIST) 1.1 Criteria for Evaluating Response in Solid Tumors

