2.0 TRIAL DESIGN

2.1 Introduction

This is a Phase I/II, non-randomized, open-label, interventional study of Pembrolizumab combined with doxorubicin for patients with advanced sarcoma. Most patients will receive this as front line therapy. As a rule, the trial is generally inclusive for most sarcoma subtypes. However, it excludes patients with prior anthracycline treatment. Patients with Ewings Sarcoma, Osteosarcoma, and some Rhabdomyosarcomas are excluded as these histologic sarcoma subtypes have well-established, evidence-based treatment paradigms combining anthracyclines with other chemotherapy.

The Phase I stage will evaluate two dose levels of doxorubicin (45 and 75 mg/m²) combined with Pembrolizumab. The 75 mg/m² doxorubicin dose is widely considered standard of care for sarcoma, as is being used as the “control” arm for recent and on-going phase III trials (NCT02451943) (Judson, Verweij et al. 2014). All patients will receive Pembrolizumab at the flat dose of 200 mg given intravenously every 3 weeks. Unless serious adverse events are observed, the Phase II expansion will combine the 75 mg/m² dose of doxorubicin with Pembrolizumab.

The phase II portion will use a two stage design treating an initial 20 patients with the combination of Doxorubicin and Pembrolizumab. If two or more objective responses are seen (either complete or partial responses), an additional 15 patients will be treated for a total of 35 patients. In summary, we expect that 44 patients will be treated on the trial (9 in the phase I portion and 35 on the phase II portion). If an additional 3 patients needed to be treated in the initial phase I cohort this could potentially increase to a maximum enrollment of 47.

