2.6 Phase II extension

[figure not shown]
The phase II extension will use a SWOG 2-stage design (modified Simon's 2 stage design) in order to detect a response rate (CR + PR) of 35%. This is based on a predicted overall response rate for single agent doxorubicin of 15%. 20 patients will be treated in the first stage. If 2 or more patients have CR or PR, an additional 15 patients will be treated. If at least 10 CR or PR's are seen, this will be considered a positive study. Patients treated in the phase I portion of the study will not be included in the phase II analysis. Any toxicity defined as a DLT for the phase I portion will also trigger a meeting of the DSMB during the phase II portion of the trial. Should 2 of these events occur, enrollment must halt until the DSMB meets.

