5.0 METHODOLOGY

5.1 Entry Criteria

This trial is designed for both male and female patients ≥ 18 years of age with unresectable sarcoma not amenable to surgery or radiation with curative intent and an ECOG performance status of 0 or 1. We expect 9 patients will be treated on the phase I dose escalation portion of the trial (it is possible as few as 6 and as many as 12 patients could be treated on the phase I portion) and 35 additional patients will be treated on the phase II expansion. All patients meeting the eligibility criterion will be considered for enrollment. No exceptions to eligibility will be granted.

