8.0 STATISTICAL ANALYSIS PLAN

8.1 Statistical Analysis Plan Summary

This is Phase I/II trial. The initial phase of the trial will use a “3+3” design. The phase II portion of the trial will use a two stage design and will not include patients treated in the phase I dose escalation for the efficacy analysis.

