8.2 Statistical Analysis Plan

Phase I Design:

The primary objective of the phase I component of this study is to evaluate the safety of Pembrolizumab given in combination with Doxorubicin among patients with advanced soft tissue sarcoma. The phase I component of this study will use a 3+3 design to evaluate the 45 mg/m² and 75 mg/m² Doxorubicin dosing in combination with Pembrolizumab. Dose-limited toxicities will be evaluated through the end of the first cycle combining Pembrolizumab with Doxorubicin.

The study design is as follows:

- Initially enroll 3 patients into the 45 mg/m² cohort
 - If 2 of 3 experience a DLT, stop and conclude that Pembrolizumab may not be given safely with Doxorubicin at the protocol-specified dose levels.
 - If 1 of 3 patients experiences a DLT, enroll 3 more patients.
 - If less than 2 of 6 experiences a DLT then initiate enrollment to the 75 mg/m² cohort.
 - If 2 or more experience a DLT, stop and conclude that Pembrolizumab may not be given safely with Doxorubicin at the protocol-specified dose levels. Should this occur, discussions will initiate with the DSMB and Merck about whether the protocol could be altered to make the regimen safe or whether the study should be halted.
 - If 0 of 3 patients experience a DLT then initiate enrollment to the 75 mg/m² cohort
- If 45 mg/m² is determined safe, enroll 3 patients into the 75 mg/m² cohort
 - If 2 of 3 experience a DLT stop and conclude that the MTD is 45 mg/m²
 - If less than 2 of 3 patients experience a DLT, enroll 3 more patients.
 - If less than 2 of 6 experience a DLT then conclude 75 mg/m² is the MTD
 - If 2 or more experience a DLT, stop and conclude that that the MTD is 45 mg/m²

The maximum sample size for the phase I component is 12 patients.

Phase II Design:

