The primary objective of the phase II design is to compare the objective response rate (ORR) with historical rates. Patients at the final phase I dose will not be included in the phase II analysis. Our null hypothesis estimates the overall response rate of single agent doxorubicin based on the EORTC randomized study of doxorubicin alone or in combination with Ifosfamide, the largest study using modern imaging and supportive care. A two-stage design with null hypothesis of 15% using a 1-sided 0.05 α level test has 85% power to detect an increase to 35%. This design requires a total of 35 patients, 20 in the 1st stage and 15 in the second stage. If 2 or more responses (CR or PR) are observed in the 1st stage, the study will continue accrual to the second stage, accruing 15 more patients. If at least 10 responses are seen out of the 35 patients (29%), then this will be considered evidence to rule out an ORR of 15% or less.

Secondary objectives include the estimation of the median PFS, time to and duration of response, and the frequency and severity of toxicities. With 51 patients, this design can estimate frequencies (and single time point estimates of PFS/OS) to within 14% with 95% confidence. The Kaplan-Meier method will be used to estimate median PFS and OS.

Correlative Endpoints: The study is not powered to detect specific hypotheses with regards to correlative endpoints, rather this data and analysis will help better identify patients having the potential to benefit from this therapy and aid in designing larger Phase III studies.

Summary statistics will be used to for describing changes across time. In addition, the time course of biomarker outcomes will be investigated graphically by summary plots or individual patient plots. Categorical data analysis and logistic regression will be used to evaluate the associations between correlative measures and clinical outcome (eg, response, clinical benefit, time to progression, progression-free survival, and survival). If there is suggestion of meaningful trend, methods such as linear mixed models may be used to characterize the pattern of change over time. Kaplan-Meier methodology and Cox Proportional Hazards models will be used to evaluate time to event endpoints.

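### The SAP's 14% precision figure is computed on 51 patients, a number the design does not contain; on the 35 phase II patients the worst case is about 17%

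*Combined protocol and SAP*

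**What the plan says.** The sentence at issue is in section 8.2, under Phase II Design, directly after the list of secondary objectives (median PFS, time to and duration of response, toxicity): "With 51 patients, this design can estimate frequencies (and single time point estimates of PFS/OS) to within 14% with 95% confidence".

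The patient counts elsewhere are:

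- **Phase II, section 8.2:** "This design requires a total of 35 patients, 20 in the 1st stage and 15 in the second stage".
- **Phase I, section 8.2:** "The maximum sample size for the phase I component is 12 patients". Section 5.1 gives the range: "it is possible as few as 6 and as many as 12 patients could be treated on the phase I portion".
- **Total, section 2.1:** 44 patients expected (9 plus 35). Three further phase I patients could make this "increase to a maximum enrollment of 47". The Trial Summary (section 1.1) repeats both figures.

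On who is analysed, section 2.6 says "Patients treated in the phase I portion of the study will not be included in the phase II analysis", and section 8.1 says the phase II portion "will not include patients treated in the phase I dose escalation for the efficacy analysis". Section 3.2 (secondary objectives) and section 5.6 (survival follow-up) do not separate the two phases. Section 5.7 lets patients who are not evaluable for response be replaced, without giving a number.

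**The concern.** The counts in sections 1.1, 2.1, 5.1 and 8.2 agree with each other. Only 51 stands apart: it is 16 above the phase II size and 4 above the stated maximum for the whole trial. The SAP gives no derivation for it.

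This is the only precision statement in section 8 for toxicity frequencies and for PFS or OS at a single time point. A reader cannot tell which patients it describes, or whether the trial can deliver it. Section 8.2 lists toxicity frequency as secondary, but section 3.1.1 makes safety and tolerability a primary objective, so the sentence also bears on a primary question.

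**Working it through.** **Inputs.** n = 51 and 14% with 95% confidence (section 8.2); phase II n = 35 (section 8.2); phase I n = 6 to 12 (sections 5.1 and 8.2); expected total 44 and maximum 47 (sections 1.1 and 2.1). A two-sided interval is assumed, as the text does not say.

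**Step 1: the plan's own figure.** The normal-approximation (Wald) half-width for a proportion is 1.96 × √(p(1 − p)/n). It is largest at p = 0.5, where it equals 0.98/√n. At n = 51 this is 0.98/7.141 = 13.7%, which rounds to the stated 14%. So 51 is the number that was used, and the formula is right.

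**Step 2: the planned counts.** With a full phase II:

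- 6 + 35 = 41
- 9 + 35 = 44
- 12 + 35 = 47

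None gives 51.

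**Step 3: the same formula on those counts.** The exact column is the largest Clopper-Pearson half-width.

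| n | Set | Wald, p = 0.5 | Difference from n = 51 | Exact |
|---|---|---|---|---|
| 51 | as stated | 13.7% | – | 14.3% |
| 47 | maximum total | 14.3% | +0.6 points | 14.9% |
| 44 | expected total | 14.8% | +1.1 points | 15.4% |
| 41 | minimum total, full phase II | 15.3% | +1.6 points | 16.0% |
| 35 | phase II only | 16.6% | +2.8 points | 17.3% |

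If phase II stopped after stage 1 (n = 20), the Wald worst case would be 21.9%.

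**Step 4: the size needed for 14.0%.** 0.25 × (1.96/0.14)² = 49 patients, 2 more than the stated maximum.

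**Step 5: where 14% still holds.** Setting the half-width to 0.14 gives p(1 − p) = n × (0.14/1.96)² = n/196. The solutions are:

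- n = 35: p up to 23% or from 77%
- n = 44: p up to 34% or from 66%
- n = 47: p up to 40% or from 60%

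**Step 6: what this means for PFS.** The documents name no time point, so this is an illustration only, with an assumed exponential curve, an assumed 12-month time point and no censoring. At n = 35:

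- Median 4.6 months (the historical doxorubicin figure in section 4.2.1): 12-month PFS = 0.5^(12/4.6) = 16.4%, half-width 12.3%.
- Median 9.2 months (an assumed doubling): 12-month PFS = 0.5^(12/9.2) = 40.5%, half-width 16.3%.

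Whether a given estimate meets 14% therefore depends on the time point and the true curve. Censoring would widen both intervals.

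**The case against.** **The effect is small.** No test, stopping rule or sample size uses 51. On the pooled reading the change is about one point or less, and 14.3% at n = 47 still rounds to 14%. At n = 35 the shortfall appears only for proportions between about 23% and 77%, and with the one median the documents give, the 12-month illustration stays inside 14%. All of this stands. It limits the consequence but does not make 51 a number in the design.

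**Replacements could explain it.** Section 2.1 builds 47 as 12 plus 35 with no allowance for replacements, while section 5.7 counts 35 as patients evaluable for response and lets others be treated in place of those who are not. The number treated could therefore pass 47. This also stands, but reaching 51 would take 4 replacements on top of the maximum total, or 16 on top of phase II alone. The documents state no such allowance, and 47 is presented as the maximum.

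**The set for PFS and OS is less open than it looks.** The sentence sits under Phase II Design, and sections 2.6, 8.1 and 8.2 keep phase I patients out of the phase II or efficacy analysis. That favours 35. Sections 3.2 and 5.6 make no phase distinction, but neither defines an analysis set. The argument is a fair one, and it points to the set with the largest shortfall. For toxicity the question remains fully open.

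**A one-sided reading.** At n = 35 a one-sided 95% limit lies 13.9% from the estimate, close to the stated figure. But the sentence names 51, for which the one-sided figure is 11.5%. Only the two-sided calculation at 51 reproduces it.

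**Conclusion.** The concern holds. The precision sentence rests on a count that matches no planned number, and the plan does not say which patients it describes. For the 35 phase II patients, the best-supported set for PFS and OS, the worst-case half-width is about 17% rather than 14%. For a pooled set of 44 to 47 treated patients it is 14% to 15%, and 15.3% if phase I enrols only 6.

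These figures assume a two-sided 95% Wald interval, p = 0.5, a completed phase II and no censoring before the time point. Exact intervals are 0.6 to 0.7 points wider at each n from 35 to 51. The effect is confined to the expected precision of descriptive estimates, including the toxicity frequencies that bear on the primary safety objective.

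**What to change.** In section 8.2:

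1. Name the analysis set for each endpoint: PFS, OS and toxicity frequencies. If phase I patients are pooled, say whether both doxorubicin dose levels are included.
2. Replace 51 with the planned size of that set and restate the worst-case precision, naming the method. For the 35 phase II patients this is within 17% with 95% confidence. For all treated patients it is about 15% at the expected 44 and about 14% at the maximum of 47.
3. If 51 was meant to include replacements under section 5.7, state the allowance and reconcile it with the maximum of 47 in sections 1.1 and 2.1.

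The cost is one or two sentences of SAP wording. Sample size, decision rules and conduct do not change. The only downside is that the stated precision becomes up to about 3 points less favourable.

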9.0 LABELING, PACKAGING, STORAGE AND RETURN OF CLINICAL SUPPLIES

9.1 Investigational Product

The investigator shall take responsibility for and shall take all steps to maintain appropriate records and ensure appropriate supply, storage, handling, distribution and usage of investigational product in accordance with the protocol and any applicable laws and regulations.

Clinical Supplies will be provided by Merck as summarized in Table 7.

Table 7 Product Descriptions

Product Name & Potency	Dosage Form
Pembrolizumab 50 mg	Lyophilized Powder for Injection
Pembrolizumab 100 mg/ 4mL	Solution for Injection

9.2 Packaging and Labeling Information

Clinical supplies will be affixed with a clinical label in accordance with regulatory requirements.

9.3 Clinical Supplies Disclosure

This trial is open-label; therefore, the subject, the trial site personnel, the Sponsor-Investigator and/or designee are not blinded to treatment. Drug identity (name, strength) is included in the label text; random code/disclosure envelopes or lists are not provided.

9.4 Storage and Handling Requirements

Clinical supplies must be stored in a secure, limited-access location under the storage conditions specified on the label.

Receipt and dispensing of trial medication must be recorded by an authorized person at the trial site.

Clinical supplies may not be used for any purpose other than that stated in the protocol.

9.5 Returns and Reconciliation

The investigator is responsible for keeping accurate records of the clinical supplies received from Merck or designee, the amount dispensed to and returned by the subjects and the amount remaining at the conclusion of the trial.

Upon completion or termination of the study, all unused and/or partially used investigational product will be destroyed at the site per institutional policy. It is the Investigator's responsibility to arrange for disposal of all empty containers, provided that procedures for proper disposal have been established according to applicable federal, state, local and institutional guidelines and procedures, and provided that appropriate records of disposal are kept.

9.6 Doxorubicin

Clinical Doxorubicin will be used and standard practices regarding storing and handling the drug will apply. More detailed information can be found in the doxorubicin package insert.

10.0 ADMINISTRATIVE AND REGULATORY DETAILS

10.1 Institutional Review Board

In accordance with federal regulations (21 CFR 312.66), an Institutional Review Board (IRB) that complies with regulations in 21 CFR 56 must review and approve this protocol and the informed consent form prior to initiation of the study.

10.2 Consent

The Principal Investigator or his associate must explain verbally and in writing the nature, duration, and purpose of the study and possible consequences of treatment. Patients must also be informed that they may withdraw from the study at any time and for any reason without jeopardizing their future treatment. In accordance with federal regulations (21 CFR 312), all patients must sign the IRB-approved consent form.

10.3 Termination of Study

The Sponsor-Investigator reserves the right to terminate this study at any time. The FDA may also terminate the study.

10.4 Compliance with Trial Registration and Results Posting Requirements

Under the terms of the Food and Drug Administration Modernization Act (FDAMA) and the Food and Drug Administration Amendments Act (FDAAA), the Sponsor-Investigator of the trial is solely responsible for determining whether the trial and its results are subject to the requirements for submission to the Clinical Trials Data Bank, <http://www.clinicaltrials.gov>. Information posted will allow subjects to identify potentially appropriate trials for their disease conditions and pursue participation by calling a central contact number for further information on appropriate trial locations and trial site contact information. Common Terminology Criteria for Adverse Events V4.0 (CTCAE)

The descriptions and grading scales found in the revised NCI Common Terminology Criteria for Adverse Events (CTCAE) version 4.0 will be utilized for adverse event reporting. (<http://ctep.cancer.gov/reporting/ctc.html>)

10.4 Response Evaluation Criteria in Solid Tumors (RECIST) 1.1 Criteria for Evaluating Response in Solid Tumors

RECIST version 1.1* will be used in this study for assessment of tumor response. While either CT or MRI may be utilized, as per RECIST 1.1, CT is the preferred imaging technique in this study.

* As published in the European Journal of Cancer:

E.A. Eisenhauer, P. Therasse, J. Bogaerts, L.H. Schwartz, D. Sargent, R. Ford, J. Dancey, S. Arbuck, S. Gwyther, M. Mooney, L. Rubinstein, L. Shankar, L. Dodd, R. Kaplan, D. Lacombe, J. Verweij. New response evaluation criteria in solid tumors: Revised RECIST guideline (version 1.1). *Eur J Cancer*. 2009 Jan;45(2):228-47.

In addition, volumetric analysis will be explored by central review for response assessment.

11.0 DATA AND SAFETY MONITORING PLAN

Institutional support of trial monitoring will be in accordance with the FHCRC/University of Washington Cancer Consortium Institutional Data and Safety Monitoring Plan. Under the provisions of this plan, FHCRC Clinical Research Support (CRS) coordinates data and compliance monitoring conducted by consultants, contract research organizations, or FHCRC employees unaffiliated with the conduct of the study. Independent monitoring visits occur at specified intervals determined by the assessed risk level of the study and the findings of previous visits per the institutional DSMP.

In addition, protocols are reviewed at least annually and as needed by the Consortium Data and Safety Monitoring Committee (DSMC), FHCRC Scientific Review Committee (SRC) and the FHCRC/University of Washington Cancer Consortium Institutional Review Board (IRB). The review committees evaluate accrual, adverse events, stopping rules, and adherence to the applicable data and safety monitoring plan for studies actively enrolling or treating subjects. The IRB reviews the study progress and safety information to assess continued acceptability of the risk-benefit ratio for human subjects. Approval of committees as applicable is necessary to continue the study.

The trial will comply with the standard guidelines set forth by these regulatory committees and other institutional, state and federal guidelines.

During the phase I portion of the trial, a data safety monitoring board will meet regularly to oversee the trial.

